5.5.2. Dropout Criteria

The following are the cases in which the subjects may request to discontinue the clinical study, or in which they may be discontinued or dropped out according to a discussion between the investigator and the sponsor.

- ① The subject or the subject's representative has withdrawn consent to participate in the clinical study.

- ② Violation of the inclusion/exclusion criteria is found during the clinical study.
- ③ Continuation of the clinical study is difficult because of adverse events or serious adverse events.
- ④ There are issues in administering the investigational product to the subject.
- ⑤ The subject is lost to follow up.
- ⑥ The subject has taken a prohibited concomitant medication, or it is determined necessary to administer a prohibited concomitant medication.
- ⑦ The subject has become pregnant during the clinical study.
- ⑧ Other cases in which the sponsor or the investigator determines that conducting the clinical study is not appropriate

For other matters related to the administration schedule of the investigational product, whether to drop out a subject will be determined based on the criteria described below.

A violation of the drug administration schedule will be treated as a minor protocol violation up to 5 times, and it will not be a condition for dropping out a subject within this limit. However, if it exceeds 5 times, the subject will be dropped out. The administration window of the drug for the first 4 weeks will be ± 3 days (however, excluding Visit 2), and thereafter, the window will be ± 5 days for the biweekly administration days. If the window of the administration day is exceeded, it will be treated and recorded as a minor violation. If the window has passed, the corresponding drug administration will be skipped and an injection will be given at the next administration day that was originally scheduled. If an injection is given before reaching the window of the administration day (e.g., at -6 days), the schedule will be adjusted by moving all subsequent administration days forward by one week. If the subject arrives at the visit day for the PSP-rating scale evaluation without 12 hours of off-medication for oral drugs that are being taken, the evaluation will be performed in that state, but it will be recorded as a minor protocol violation. However, the off-medication evaluation rules shall be followed for the remaining visit days.

5.5.3. Protocol Violations

The principal investigator and staff members of this clinical study shall fully understand and thoroughly implement the protocol to prevent violations of the protocol. To comply with the administration and test schedule of the investigational product in this clinical study, the site staff shall provide written notifications or make telephone calls regarding the study site visit schedule to allow the subjects to make visits on the applicable days without omission. However, protocol violations that occur unavoidably will be handled as shown below.

In the case of major protocol violations, the corresponding subject will be dropped out from the analysis (excluded from the per-protocol set) as a rule, and the applicable situations are as follows:

- ① Informed consent form was not obtained.
- ② The inclusion/exclusion criteria were violated.
- ③ Prohibited concomitant medications were administered during the clinical study.
- ④ The PSP-rating scale test of Visit 1 (screening), which is the first visit of this study, and Visit 16 (Week 26) were missed.

Other minor protocol violations that are judged as having no impact on the interpretation of the clinical study results will be included in the per-protocol set analysis by accurately describing the extent of violation or delay and the reason, and comprehensively considering whether the clinical study has been affected through a blind meeting prior to database lock.

5.5.4. Handling of Dropouts and Protocol Violations

Any of these situations shall be documented in the subjects' case report forms and source documents. For subjects who have been dropped out, the relevant reason will be recorded in the Clinical Trial Completion section of the case report form. Even if a subject has been dropped out, the results of previous tests shall be included in the analysis.

In the case of a subject who has been dropped out because of an adverse event, the subject will be followed up

until the subject recovers to the state prior to investigational product administration or to the baseline, or until the principal investigator can determine that the adverse event has normalized.

After randomization, subjects who discontinue participating in the clinical study or drop out, regardless of the reason, shall not be replaced.

6. Details of Clinical Study Design

6.1. Clinical Study Duration

Approximately 24 months from the approval date of the Ministry of Food and Drug Safety and the Institutional Review Board (IRB) of the study site

Subject enrollment duration: Approximately 10 months

- Duration of participation for each subject: Approximately 8 months (32 weeks in total—4 weeks for screening, 24 weeks for treatment, 4 weeks for safety follow-up)
- Data management, statistical analysis, and completion of clinical study report after the end of study: Approximately 6 months

However, the planned duration of study may be extended or shortened depending on the speed of subject enrollment, changes in the procedures after the end of study, etc.

6.2. Design of Clinical Study

[figure not shown]
This is a 24-week, multicenter, randomized, double-blind, placebo-controlled, parallel design, prospective, Phase 2a exploratory clinical study.

If the subject and/or the subject's representative provide a written consent to participate in this clinical study, the required examinations and tests will be performed at the screening visit, and the screening period will run for 4 weeks or shorter.

Subjects who are ultimately determined as eligible by the inclusion/exclusion criteria after screening will be randomized at a 1:1:1 ratio to Study Group 1 (GV1001 0.56 mg/day), Study Group 2 (GV1001 1.12 mg/day), or the placebo group depending on the study site in which they are enrolled. Depending on the randomization results, subjects will be administered the investigational product (study drug or placebo) once weekly for the first 4 weeks (1 month), and then administered 10 times at 2-week intervals for 20 weeks (5 months) for a total of 14 doses over 24 weeks (6 months).

All subjects will visit the study site according to the planned clinical study schedule to receive the investigational product and to be evaluated for efficacy and safety. To ensure the objectivity and accuracy of the study results, the efficacy evaluators evaluating the PSP-rating scale will be limited to neurologists who have been sufficiently educated and trained, and the collection of efficacy and safety evaluation data and biomarkers will be performed in a consistent order at each visit.

※ Neurological drugs administered at a stable dose for at least 1 month prior to a subject's participation in this clinical study (prior to screening) will be continued without changing the dose during the clinical study participation period.

[Clinical Study Schematic]

6.3. Randomization

Subjects who provide a written consent to participate in this clinical study will be assigned a screening number consisting of [study site number: 2 digits]-S-[serial number: 3 digits] in the order in which the written consent was obtained. Subjects who meet the inclusion and exclusion criteria will then be randomized according to the randomization plan, and will be assigned a unique randomization number consisting of [study site number: 2 digits]-R-[serial number: 2 digits] in the order in which the investigator decided to enroll the subjects. Subjects who meet the inclusion and exclusion criteria will be assigned sequentially according to the order of randomization at each study site.

A randomization table will be generated by an independent statistician not related to this clinical study prior to the start of the clinical study by using SAS® (Version 9.4 or higher; SAS institute, Cary, NC, USA), and the table will be generated to allow assignment of subjects to Study Group 1, Study Group 2, or the control group at a 1:1:1 ratio by applying a stratified block randomization method. Subjects who are enrolled in this clinical study and ultimately determined to be eligible to participate in the clinical study will be assigned a randomization number sequentially through the Interactive Web Response System (IWRS), and afterward, the subjects will be assigned to Study Group 1, Study Group 2, or the control group and receive a unique IP number.

6.4. Blinding and Unblinding

To maintain double-blinding, a placebo that is indistinguishable from the investigational product in appearance will be used in this clinical study. In addition, the exterior of the investigational product container will be masked using an opaque plastic cover and sticker, and a label will be affixed on the surface to ensure that double-blinding is strictly maintained. However, to minimize the possibility of unblinding the investigator and the subjects in the management, transfer, preparation (diluting lyophilized powder in normal saline), and administration processes of the investigational product at the study site, the management of the investigational product shall be conducted as described below.

- For each study site, a clinical trial pharmacist who manages the investigational product, a person in charge of diluting the investigational product, and a person in charge of administration will be designated in advance.
- Dilution and administration of the investigational product may only be performed by a designated individual, and the person in charge of dilution and administration should be distinguished.
- The person in charge of dilution and administration shall be trained in advance on the dilution and management of the investigational product and shall have a training log.

Furthermore, to maintain double-blinding, the details of assigning unique codes to each group will not be disclosed until the end of the clinical study.

The details of assigning unique codes to each group will be managed by the Interactive Web Response System (IWRS) of the central registration center. In principle, the randomization codes shall maintain a blinded state for the treatment group assignment of each subject until the database lock is completed after the end of the clinical study (completion of the blinded study period for all subjects or dropping out of all subjects).

Double-blinding may be unblinded in the case that viewing of the relevant codes is inevitably necessary due to the occurrence of emergency situations such as serious adverse drug reactions, or if the sponsor determines that it is absolutely necessary for the rights, interests, and safety of the subjects. When double-blinding is unblinded, management will be conducted to allow only the viewing of the unique codes of relevant subjects.

Unblinding shall be considered on a case-by-case basis and only in the event of a serious medical emergency. In general, blinding shall be unblinded only if the information on the treatment group affects the subjects' treatment. If the principal Investigator or the sponsor deems it is necessary to unblind, the sponsor or the principal investigator will be contacted to obtain consent for unblinding, and then the principal investigator or the sponsor

will unblind. In this case, the unblinding will be recorded and kept as a document. Subjects whose randomization codes have been unblinded may not continue in this clinical study and will be handled as dropouts.

7. Criteria for Study Termination and Early Discontinuation

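### Section 6.4 reserves unblinding for serious medical emergencies yet requires consent before the code is opened, with no stated exception, and its two paragraphs disagree on when the code may be broken

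*Combined protocol and SAP*

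**What the plan says.** Protocol section 6.4 deals with unblinding of individual subjects in two places.

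The earlier paragraph gives two triggers. The first is that seeing the code is "inevitably necessary due to the occurrence of emergency situations such as serious adverse drug reactions". The second applies "if the sponsor determines that it is absolutely necessary for the rights, interests, and safety of the subjects". This paragraph mentions no consent step, and it does not tie the second trigger to an emergency. The section also places the codes in the IWRS of the central registration center and limits what may be viewed to the codes of the subjects concerned.

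The closing paragraph is narrower: "Unblinding shall be considered on a case-by-case basis and only in the event of a serious medical emergency". It adds that, in general, "blinding shall be unblinded only if the information on the treatment group affects the subjects' treatment". It then sets out a procedure. "If the principal Investigator or the sponsor deems it is necessary to unblind", then "the sponsor or the principal investigator will be contacted to obtain consent for unblinding", "and then the principal investigator or the sponsor" opens the code. The break is documented, and the subject may not continue and is counted as a dropout.

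**The concern.** An emergency code break exists so that a physician can learn the allocation when it changes what is done for the patient. The closing paragraph accepts that purpose, since it ties a break to the allocation mattering for treatment. It then makes the break wait for another party's agreement. If the step is followed as written, information that the protocol itself regards as relevant to treatment can be held up, and nothing says what happens if the other party does not answer in time.

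The second problem is internal. One paragraph lists a sponsor-determined trigger that needs no emergency; the other says that only an emergency will do. Site staff, the IWRS provider and an auditor could each apply a different rule.

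**Working it through.** There is no figure to reproduce. The check is a reading of the text.

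**1. Order of events.** The closing paragraph gives three steps: a party judges unblinding necessary ("If the principal Investigator or the sponsor deems it is necessary to unblind"); contact is made and consent obtained ("the sponsor or the principal investigator will be contacted to obtain consent for unblinding"); the code is opened ("and then the principal investigator or the sponsor"). The text asks for consent rather than notification, and consent comes before the break.

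**2. Whose consent.** The first step names the principal investigator, then the sponsor. The second names the sponsor, then the principal investigator. The reversed order suggests that each contacts the other. That is an inference, because the paragraph does not spell it out. Under it, an investigator's request needs the sponsor's agreement.

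**3. Search for an exception.**

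| Place | What it adds |
|---|---|
| Protocol 6.4, earlier paragraph | Names emergencies as a trigger; neither repeats nor waives the consent step; describes no direct investigator access to the IWRS |
| Protocol 10.5.2 to 10.5.4 (AE, SAE and SUSAR reporting) | No unblinding route |
| Protocol 11.2.4.1 and 11.2.4.2 (IDMC, safety monitoring) | No unblinding route |
| Protocol 13.5.1 and 13.5.2 (urgent changes and departures) | Waive prior IRB or Ministry approval; do not mention sponsor consent or access to codes |
| SAP 4.2 | Unblinding after database lock only |

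No exception is stated in any of them.

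**4. The two sets of conditions side by side.**

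| Condition | Earlier paragraph | Closing paragraph |
|---|---|---|
| Emergency | Yes | Yes |
| Sponsor's determination, no emergency | Yes | No, since it says "Unblinding shall be considered on a case-by-case basis and only in the event of a serious medical emergency" |
| Consent first | Not mentioned | Required |

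The second row is a direct conflict. The third leaves it unclear whether the consent step governs every break.

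**5. Reach into the primary endpoint.** An unblinded subject becomes a dropout (6.4). Dropouts are asked to attend a last visit with the Visit 16 tests (5.5.1), which include the PSP-rating scale (10.2.9). SAP 6.3 uses efficacy data from such a visit only if it falls within a regular visit's window. The scale is scheduled after baseline at Visits 10 and 16 (protocol 10.3.12). SAP 6.2 gives these visits days 87 to 97 (97 − 87 + 1 = 11 days) and days 171 to 181 (181 − 171 + 1 = 11 days). Assuming that only scheduled rating visits enter the model, at most one post-break rating per unblinded subject could count, and only if it fell in one of these two 11-day windows. Section 6.4 does not say who at the site may learn the allocation, so it does not expressly keep it from the rater.

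**The case against.** The strongest reply is that the earlier paragraph's emergency trigger carries no consent step and can stand as its own route. That reading is possible, but the closing paragraph also concerns emergencies and gives the only procedure in the section. A reader in a hurry cannot tell which governs, so the reply supports clarification.

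Protocol 13.5.2 allows the principal investigator or a sub-investigator to depart from the protocol to remove an immediate risk. It might excuse someone who skipped the consent step. It does not provide access to the code, and the approval it dispenses with is the IRB's.

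An IWRS manual may also give investigators direct access, and contact pages were removed from the documents reviewed. Both points stand as limits on what can be said about practice. The protocol would still call for consent first.

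A reader might infer more than the text supports:

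- *That every permitted code break is an emergency.* The earlier paragraph's sponsor trigger contradicts this.
- *That both parties learn the allocation each time, or that a sponsor-side break hands it to the site.* Consent is not disclosure. The paragraph has one party or the other open the code and does not say that the consenting party is told the result.
- *That sub-investigators have no route at all.* The paragraph names only the principal investigator, but nothing stops a sub-investigator from acting through that person.
- *That the wait would run overnight or over a weekend.* The documents support no length of delay, and the absence of a round-the-clock contact cannot be inferred from pages that were removed.
- *That the blind for the primary endpoint is seriously weakened.* Unblinded subjects leave the study, and what remains is the single windowed rating described above.

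**Conclusion.** The point holds in two parts. First, the closing paragraph of 6.4 reserves unblinding for serious medical emergencies and puts consent before the break, and neither document states an exception for urgency or for a party who cannot be reached. That the consent is the other party's is the natural reading, not an explicit statement. Second, the two paragraphs conflict on whether the sponsor may break the blind without an emergency.

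The size cannot be put as a number. The rule covers all 75 planned subjects, but the documents give no expected count of code breaks and no basis for a delay. The consequence is mainly for patient safety. For the primary analysis it is small: at most one possibly unblinded rating per unblinded subject, and only if the last visit falls in a rating window and the evaluator has been told the allocation.

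**What to change.** In protocol section 6.4:

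- Reconcile the two paragraphs so that one list of permitted triggers applies, and state for each whether consent is needed.
- State that, for an emergency break, the principal investigator or a delegated investigator may open that one subject's code through the IWRS without prior sponsor consent.
- Replace prior consent in that case with prompt notification to the sponsor that the code was opened, without revealing the allocation.
- Require the IWRS to log who opened the code, when and why.
- State that the allocation is not passed to the PSP-rating evaluator, so that any last-visit rating stays blinded.

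This concerns access to the code only; it leaves the treatment of any emergency to the clinicians. The cost is protocol wording and an IWRS user-rights setting. The downside is a small risk of avoidable code breaks, each of which would turn a subject into a dropout under the present rule. The existing emergency criterion and the log limit that risk.

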7.1. Termination Criteria

When the procedures of Visit 16 (Week 26), which is the subjects' Week 24 (6 months) efficacy evaluation visit, are completed after starting investigational product administration, this clinical study will be deemed completed. However, if there are adverse events that have not disappeared at Week 24 weeks (6 months), safety follow-up will be performed until Week 28 (7 months) thereafter, or if possible, until the corresponding adverse events disappear. This will be conducted either by the subject visiting the study site in person or by the investigator or the investigator's delegatee calling the subject over the telephone to collect relevant information such as whether the adverse event has disappeared and the date of resolution.

The termination visit of the last enrolled subject is defined as the end of the entire clinical study.

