10.2.10. Visit 17 (End-of-Study Visit, Week 28 ± 5 days)

This is the study termination visit, which will be conducted over the telephone.

- Changes in the prior/concomitant drug administration history will be checked compared with the previous visit.
- The occurrence of adverse events since the previous visit and their details will be investigated.

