10.5.2. Reporting of Adverse Events

- Adverse events will be collected during the clinical study from the time point after investigational product administration and up to the final visit. All medical events that occur prior to investigational product administration will be recorded as medical history.
- Adverse events shall be reported by including the name of the adverse event, duration (start date and disappearance date), severity, causal relationship to the investigational product, actions taken for the investigational product, outcome, corrective treatment for the adverse event, and whether the event is a serious adverse event.
- When recording an adverse event, the investigator shall use a comprehensive diagnosis or symptom using standard medical terminology rather than recording each symptom or sign.
- Adverse events that occur during the clinical study shall be followed up until they disappear, show stable outcomes, or the subject is lost to follow-up.
- Adverse events that occur after the end of the clinical study shall be reported only if they are serious and related to the investigational product.

1) Severity Assessment

The investigator will assess the severity of adverse events and serious adverse events by referring to the criteria described below.

Mild	The event causes minimal discomfort without interfering with the subject's normal daily life (function), and it can be easily tolerated by the subject.
Moderate	The event causes discomfort that significantly interferes with the subject's normal daily life (function).

Severe The event makes the subject's normal daily life (function) impossible.

Activities of daily living are defined below.

: All activities that occur in daily life to take care of one's own body (e.g., bathing, dressing and undressing, eating, taking medications, hygiene, and personal care)

An adverse event or serious adverse event can both be evaluated as severe according to the definition above, and one should not be confused for the other since a severe adverse event does not necessarily correspond to a serious adverse event.

2) Causality Assessment

The investigator will assess the causal relationship between an adverse event and the investigational product by referring to the criteria described below. If it is assessed as unlikely, it can be determined as "no causal relationship" (non-ADR). If it is assessed as other items, it will be determined that there is a causal relationship (ADR).

- ① Certain

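### Protocol 7.1 ends a subject's study at Visit 16 and follows only unresolved adverse events to Week 28, which contradicts the Visit 17 contact scheduled for every subject

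*Combined protocol and SAP*

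**What the plan says.** Protocol 7.1 makes three statements about the end of the study.

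- Once the Visit 16 (Week 26) procedures "are completed after starting investigational product administration, this clinical study will be deemed completed".
- It then adds that "if there are adverse events that have not disappeared at Week 24 weeks (6 months), safety follow-up will be performed until Week 28", or longer if possible. That contact, in person or by telephone, gathers information such as "whether the adverse event has disappeared and the date of resolution".
- For the trial as a whole, "The termination visit of the last enrolled subject is defined as the end of the entire clinical study".

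Protocol 10.2.10 describes Visit 17 at Week 28: "This is the study termination visit, which will be conducted over the telephone". Its tasks include this one: "The occurrence of adverse events since the previous visit and their details will be investigated". Section 10.2.9 has the site book that call at Visit 16. Neither section makes the call depend on AE status. Section 6.1 allots each subject 4 weeks of screening, 24 of treatment and 4 of safety follow-up. The SAP 6.2 visit table labels Visit 17 as EOS.

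Sections 10.5.2 and 10.5.3 collect AEs and SAEs from dosing to the final visit, without giving that visit a number. For the time afterwards, 10.5.2 says: "Adverse events that occur after the end of the clinical study shall be reported only if they are serious and related to the investigational product". Section 10.5.3 repeats the rule.

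Under 10.2.9 and 10.3.17 the second CSF sample is taken at Visit 16, only from subjects who consented to it separately.

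**The concern.** The two sets of passages lead to different safety data. If Visit 17 is the final visit, every new AE up to Week 28 is collected in every subject. If Visit 16 completes the study, a subject with no open AE at that point has no further contact under 7.1, and the narrower end-of-study rule in 10.5.2 may be applied to anything that starts later.

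Section 7.1 is also at odds with itself. It completes the study at Visit 16 but ends the whole trial at a termination visit, which 10.2.10 identifies as Visit 17. Section 5.5.1 adds to the uncertainty, because it asks dropouts to come for a last visit at which the Visit 16 tests are done.

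What is at stake is the completeness of AE data in the second half of the planned post-dose follow-up, which begins right after an invasive sample in some subjects, and whether sites collect those data in the same way.

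**Working it through.** **Inputs.** Analysis windows from SAP 6.2: Visit 15 (last dose) Days 157–167, Visit 16 Days 171–181, Visit 17 Days 185–195. Planned participation from protocol 6.1: 4, 24 and 4 weeks.

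**1. The plan's own figure.** 4 + 24 + 4 = 32 weeks, as 6.1 states. The window midpoints are (157 + 167)/2 = 162, (171 + 181)/2 = 176 and (185 + 195)/2 = 190. From the last dose to Visit 17 is 190 − 162 = 28 days, or 4 weeks. The stated follow-up is therefore reproduced only if Visit 17 applies to every subject.

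**2. The same figure under 7.1.** For a subject with no unresolved AE, follow-up after the last dose is 176 − 162 = 14 days, or 2 weeks. Participation becomes 4 + 24 + 2 = 30 weeks, which does not match 6.1.

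**3. The disputed interval.** Visit 16 to Visit 17 is 190 − 176 = 14 days, and 14/28 = 50% of the post-dose period. Within the windows it runs from 185 − 181 = 4 days to 195 − 171 = 24 days. As a share of the whole nominal AE period it is 14/(190 − 1) = 7.4%.

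**4. What is recorded for an event that starts in that interval**, in a subject with no open AE at Visit 16:

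| Event | Visit 17 is the final visit (10.2.10) | Visit 16 is taken as the end (7.1) |
|---|---|---|
| Non-serious, related or not | collected | not required |
| Serious, judged unrelated to the product | collected | not required |
| Serious and related to the product | collected | still reportable |

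A complication of the Visit 16 CSF collection that appears after the visit would normally fall in one of the first two rows.

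**5. The trigger in 7.1.** The check for unresolved AEs is set at Week 24 (6 months). Visit 15 is at Week 24. Visit 16 is at Week 26, but 7.1 and 10.2.9 call it the Week 24 (6 months) efficacy evaluation. The sentence before the trigger uses the label in that second sense, so Visit 16 is the more natural reading, but the text allows both. If Visit 15 were meant, an AE that began between the last dose and Visit 16 would not trigger follow-up.

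**6. Effect on the planned analyses.** SAP 10.2.2.1 and protocol 11.2.10.1 compare AE incidence as subjects with an event. SAP 10.2.2 also reports numbers of events, SAE and adverse drug reaction (ADR) incidence, and tables by system organ class (SOC) and preferred term (PT). The treatment-emergent AE definition in SAP 10.2.1 has no end date, so the SAP does not settle which visit closes collection. A subject with an open post-dose AE already counts in any-AE incidence, and longer follow-up cannot count that subject again. Event counts, SAE and ADR incidence, and SOC/PT rows can change with the length of follow-up.

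**The case against.** The strongest reply is that the protocol as a whole points to Visit 17. Sections 6.1, 10.2.9 and 10.2.10, the schedule tables and SAP 6.2 all do so, and 7.1 itself ends the trial at the termination visit. Section 7.1 sets no limit on AE reporting and does not forbid recording a new event. Most sites would probably make the scheduled call and ask the scheduled questions. This stands, and it makes the loss a risk at sites that follow 7.1 rather than a certain result of the plan.

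A reader might infer four stronger conclusions that the documents do not support.

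- *That 7.1 excludes serious complications of the CSF collection.* The exclusion arises only if Visit 16 is taken as the end of the study under 10.5.2 and 10.5.3. Events that are both serious and product-related remain reportable even then, and the point concerns only subjects who consented to CSF sampling.
- *That following only subjects with open AEs biases the comparison of any-AE incidence.* Those subjects are already counted, as step 6 shows. The 7.1 contact is described in terms of resolution status and date, so it is also not clear that it would find new events.
- *That the unresolved-AE check is fixed at the last-dose visit.* The label is ambiguous and favours Visit 16.
- *That the lost follow-up can be counted in subject-days or events.* This would need the share of subjects with an open AE at Visit 16, the AE rate in the interval and the number of sites following 7.1. The documents give none of these.

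**Conclusion.** The contradiction is real, and nothing in the protocol or SAP says which section governs. At a site that follows 7.1, new non-serious events and serious events judged unrelated to the product could go unrecorded between Visits 16 and 17, in subjects with no unresolved AE. The interval is nominally 14 of 28 post-dose days, or 50%, and 4 to 24 days within the windows. These figures use the SAP 6.2 window midpoints and limits, and count follow-up from the last dose at Visit 15.

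Event counts, SAE and ADR incidence and SOC/PT rows could be affected. No number of lost events can be given, and no efficacy result or sample size depends on the point. It is an internal inconsistency that should be corrected, with a limited but avoidable effect on safety data.

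**What to change.** Reconcile 7.1 with 6.1, 10.2.9, 10.2.10 and SAP 6.2 so that one numbered visit ends AE and SAE collection for all subjects, whether or not an AE is open. The schedule already provides Visit 17 for everyone.

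In 10.5.2 and 10.5.3, tie both the final visit and the end of the clinical study to that numbered visit, per subject. In the unresolved-AE clause of 7.1, replace the Week 24 label with a visit number.

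The cost is a protocol wording amendment. It adds no visit and no assessment to the existing schedule.
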